14.1. DERIVATIONS

- Duration of exposure (days)
Last dose of study drug – First dose of study drug + 1.
- Person years of exposure
Sum of total exposure (days) for all subjects within each treatment group / 365.25
- Overall number of tablets taken
Sum of number of dispensed tablets – Sum of number of returned tablets, if any returned tablets is missing then overall number of tablets taken is set to missing

15. STUDY DRUG COMPLIANCE

Compliance to study drug will be presented for the SAF population.

Percent compliance will be calculated by visit and overall on the number of subjects with non-missing compliance data. For each postbaseline visit, if the number of tablets returned is missing, the corresponding compliance will be set as missing. Overall compliance will be set to missing if one or more blister cards are not returned to the site for accountability.

Non-compliance is defined as less than 75% or more than 125% non-missing compliance. Subjects with missing compliance will not be classified as non-compliant but described in the categorical analysis.

Compliance will be summarized both as a continuous variable (ie, mean percentage) and categorically (ie, number and percentage of subjects who are compliant vs. non-compliant, or with compliance $< 75\%$, $75\% - 125\%$, $> 125\%$, and missing).

Subject level treatment compliance will be listed.

Document:

Author:

Version Number:

V2.0

Version Date:

21MAY2020

Template No: CS_TP_BS016 Revision 4
Effective Date: 01Apr2016

Reference: CS_WI_BS005

15.1. DERIVATIONS

Compliance with study drug will be calculated for each period defined by study visits (ie, per-visit compliance) and overall.

Per-visit compliance for the period defined by visit (V-1) and visit V will be calculated as:

$$\frac{\# \text{ Tablets dispensed at Visit (V-1)} - \# \text{ Tablets returned at Visit V}}{\# \text{ Tablets should be taken per day} \times (\text{Date of Visit V} - \text{Date of Visit (V-1)})} \times 100\%$$

Two tablets per day are supposed to be taken. If number tablets dispensed at Visit (V-1) and/or number tablets returned at Visit V are missing, per-visit compliance will not be calculated for the period impacted.

If a subject discontinued from the study in between Visit (V-1) and Visit V, then the above formula will be modified to:

$$\frac{\# \text{ Tablets dispensed at Visit (V-1)} - \# \text{ Tablets returned at Visit ET}}{\# \text{ Tablets should be taken per day} \times (\text{Date of Visit ET} - \text{Date of Visit (V-1)})} \times 100\%$$

The per-visit compliance calculated above will contribute to the summary of per-visit compliance for the period defined by visit (V-1) and visit V.

Overall compliance will be calculated as:

$$\frac{\text{Total } \# \text{ tablets dispensed} - \text{Total } \# \text{ tablets returned}}{\# \text{ Tablets should be taken per day} \times \text{Duration of Exposure}} \times 100\%$$

Duration of exposure is calculated as specified in [Section 14.1](#).

If number tablets dispensed and/or number tablets returned are missing at 1 or more visits, overall compliance will not be calculated.

16. EFFICACY OUTCOMES

16.1. PRIMARY EFFICACY

Impact of the COVID-19 pandemic on efficacy will be investigated using additional sensitivity analyses (see [Section 16.1.4.4](#), [Section 16.1.4.5](#), [Section 16.2.4](#), [Section 16.3.3.5](#) and [Section 16.3.3.6](#)). Additional adhoc analysis may be conducted after DB lock to further investigate the COVID-19 impact.

16.1.1. PRIMARY EFFICACY VARIABLE & DERIVATION

The primary efficacy endpoint is the change from baseline in the MADRS total score at Week 6.

The MADRS is a clinician-rated assessment of the subject's level of depression. The measure contains 10 items that measure apparent and reported sadness, inner tension, reduced sleep and appetite, difficulty concentrating, lassitude, inability to feel, and pessimistic and suicidal thoughts. Each item is scored in a range of 0 to 6 points, with higher scores indicating increased depressive symptoms. Total

Document:

Author:

Version Number:

V2.0

Version Date:

21MAY2020

Template No: CS_TP_BS016 Revision 4
Effective Date: 01Apr2016

Reference: CS_WI_BS005

score will be equal to the sum of the 10 items (range between 0 and 60). MADRS is assessed at Visit 1/Screening, Visit 2/Baseline/Week 0, Visit 3/Week1, Visit 4/Week 2, Visit 5/Week 4, and Visit 6/Week 6.

16.1.2. MISSING DATA METHODS FOR PRIMARY EFFICACY VARIABLE

The MADRS total score at a visit will be set to missing at that visit if any one item is missing. The primary efficacy variable, change from baseline in MADRS score at Week 6, will be set to missing if MADRS score at Week 6 is missing or baseline value is missing. The same applies to all other visits.

The primary analysis of the primary efficacy variable will use an MMRM which makes an MAR assumption to the missing primary efficacy endpoints. Early termination data will be mapped as described in [Section 6.3](#). Missing data will not be imputed.

16.1.3. PRIMARY ANALYSIS OF PRIMARY EFFICACY VARIABLE(S)

The primary efficacy estimand is defined as the efficacy of each SEP-4199 dose over placebo for 6 weeks, calculated as the difference in the primary efficacy endpoint between each SEP-4199 treatment group and the placebo treatment group in the ITT population. This estimand, which will only include those subjects who participate at sites located in the US and Europe, provides an estimate of the efficacy of each SEP-4199 dose over placebo, should a subject be able to tolerate and adhere to treatment for 6 weeks.

The 4 attributes of the primary efficacy estimand are as follows:

- A. **Population of interest:** ITT subjects with major depressive episode associated with bipolar I disease (bipolar I disorder) at sites located in the US and Europe defined through the inclusion/exclusion criteria.
- B. **The variable of interest (endpoint):** change from baseline in MADRS total score at Week 6
- C. **Intercurrent events (and how to handle them)**

The estimand is based on the effect of treatment in the hypothetical absence of any intercurrent events, ie, if all subjects had adhered to treatment up to Week 6. This includes events where a subject continues the study regardless of the intercurrent event(s) (eg, subject received a prohibited medication during the treatment period and was not discontinued from the study) and/or events that cause the subject to discontinue from the study.

Any intercurrent event where subject continues the study regardless of the intercurrent event will be ignored for the primary analysis and the primary efficacy data will be analyzed as is.

The statistical analysis for intercurrent events that lead to treatment discontinuation rests on an assumption about measurements that would have been observed under the hypothetical setting where a subject does not discontinue from treatment. For example, a subject who discontinues treatment before Week 6 in the SEP-4199 treatment group is assumed to behave similar to a subject who completes the study up to Week 6 in the same SEP-4199 treatment group using the MMRM analysis based on the MAR assumption. The assumption for subjects in the placebo group is made similarly. However, as such assumptions cannot be verified, sensitivity analyses will be conducted to assess the

Document:

Author:

Version Number:

V2.0

Version Date:

21MAY2020

Template No: CS_TP_BS016 Revision 4
Effective Date: 01Apr2016

Reference: CS_WI_BS005

robustness of the conclusions, as indicated in [Section 16.2.4](#).

D. Population level summary of the variable: Difference in means of change from baseline in MADRS total score at Week 6 comparing each SEP-4199 treatment group to placebo

The efficacy of SEP-4199 in terms of the MADRS total score will be evaluated using the following two null hypotheses:

H1: There is no difference in mean change from baseline at Week 6 on the MADRS total score in the SEP-4199 200 mg treatment arm compared to Placebo.

H2: There is no difference in mean change from baseline at Week 6 on the MADRS total score in the SEP-4199 400 mg treatment arm compared to Placebo.

The alternative hypothesis for each of the null hypotheses is that there is a difference. If at least 1 of the primary treatment group comparisons demonstrate a significant result, the study will be considered positive.

The primary efficacy endpoint will be analyzed for the ITT population using an MMRM analysis, with change from baseline in the MADRS total score as the response variable and with factors for treatment group, week, region, baseline MADRS total score, and the treatment-by-week interaction. This analysis method makes an MAR assumption to the missing primary efficacy endpoints. The Kenward Roger approximation will be used to estimate denominator degrees of freedom. An unstructured covariance matrix will be used for the within-subject correlation. A robust sandwich estimator for the standard error of the fixed effects ([Diggle 2002](#)) along with a spatial exponential or a spatial power covariance structures will be assumed sequentially in case the model fails to convergence. The first covariance structure to yield convergence will be used in the analysis.

The Least Square (LS) mean treatment differences (each SEP-4199 group minus placebo) of change from baseline at Week 6, their 2-sided 95% CIs, and the associated p-values will be calculated based on the MMRM. The LS mean of change from baseline over time will be plotted. Adjusted p-values will be calculated using a truncated Hochberg procedure with gamma parameter=0.9 (See [Section 7.4](#)).

At each postbaseline visit, within-group and between-group effect-size will be presented. Within-group effect size will be calculated as the absolute value of LS mean of change from baseline divided by SD, obtained as the SE of the LS Mean multiplied by the square root of the treatment group change from baseline sample size at each visit. Based on the MMRM, between-group effect size at a visit will be calculated as the absolute value of the LS means difference from placebo divided by the model estimate of the pooled SD at the visit, which is obtained from the square root of the diagonal element, associated at the visit, from the covariance matrix (R matrix of subjects with MADRS total score at all visits).

Multiplicity adjustment to control the global family wise Type I error rate at 5% is described in [Section 7.4](#).

The normality and homoscedasticity assumptions underlying the primary MMRM model will be assessed graphically and included in the SAS outputs. Shapiro-Wilk statistic will be included in the SAS output for exploratory purposes. Marginal studentized and Pearson residuals will be plotted against the predicted values, respectively, and quantile-quantile (Q-Q) plots of these residuals versus the expected quantiles of the standard normal distribution will be included in the SAS outputs to provide a graphical view of similarity and difference in the 2 distributions. Additional analyses may be explored to better understand the potential impact of any deviations on the interpretation of the primary efficacy analysis.

Document:

Author:

Version Number:

V2.0

Version Date:

21MAY2020

Template No: CS_TP_BS016 Revision 4
Effective Date: 01Apr2016

Reference: CS_WI_BS005

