15.3.5.1. Primary Efficacy Endpoint Analysis

The primary efficacy endpoint is the change from baseline in the MADRS total score at Week 6.

The primary efficacy estimand is defined as the efficacy of each SEP-4199 dose over placebo for 6 weeks, calculated as the difference in the primary efficacy endpoint between each SEP-4199 treatment group and the placebo treatment group in the ITT population. This estimand, which will only include those subjects who participate in sites located in US and Europe, provides an estimate of the efficacy of each SEP-4199 dose over placebo, should a subject be able to tolerate and adhere to treatment for 6 weeks.

The efficacy of SEP-4199 in terms of the MADRS total score will be evaluated using the following two null hypotheses:

H1: There is no difference in mean change from baseline at Week 6 on the MADRS total score in the SEP-4199 200 mg treatment arm compared to Placebo.

H2: There is no difference in mean change from baseline at Week 6 on the MADRS total score in the SEP-4199 400 mg treatment arm compared to Placebo.

The alternative hypothesis for each of the null hypotheses is that there is a difference, respectively. If at least, one of the primary comparisons demonstrate a significant result, the study will be considered positive.

The primary efficacy endpoint will be analyzed for the ITT population by means of an MMRM analysis, with change from baseline in the MADRS total score as the response variable and with factors for treatment group, visit, region, baseline MADRS total score, and the treatment-by-visit interaction. This analysis method makes a missing at random (MAR) assumption to the missing primary efficacy endpoints. The Kenward Roger approximation will be used to estimate denominator degrees of freedom. An unstructured covariance matrix will be used for the within-subject correlation. A robust sandwich estimator for the standard error of the fixed effects (Diggle 2002) along with a spatial exponential or a spatial power covariance structures will be assumed sequentially in case of a convergence problem. The first covariance structure to yield convergence will be used in the analysis.

The Least Square (LS) mean treatment differences (each SEP-4199 group minus placebo) of change from baseline at Week 6, their 2-sided 95% CIs, and the associated p-values will be calculated based on the MMRM.

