5.2. PER PROTOCOL [PP] POPULATION

The per protocol (PP) population will consist of all ITT subjects who have no important protocol deviations (IPD), as determined during the IPD review meetings, that may affect the interpretation of the primary efficacy endpoint as defined in [Section 2.6.1](#). See [APPENDIX 7](#) for specifications of IPD. New IPD categories may be created through the review of investigator comments and/or protocol deviations log. The predefined and any new IPDs are defined during the Blinded Data Review (BDR) Process. See [APPENDIX 6](#) for specifications of the BDR Process. Subjects in the PP population will be analyzed according to their randomized treatment group.

Analysis of the primary and the secondary efficacy endpoints will also be performed using the PP population and analyzed according to the randomized treatment group.

Document:

Author:

Version Number:
Version Date:

V2.0

21MAY2020

Template No: CS_TP_BS016 Revision 4
Effective Date: 01Apr2016

Reference: CS_WI_BS005

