16.1.5.2. Analysis on the per protocol population

The primary MMRM analysis will be repeated for the PP population to examine the impact of protocol deviations.

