16.2.3. ANALYSIS OF SECONDARY EFFICACY VARIABLE

The secondary efficacy estimand for this study is the difference in means of change from baseline in the CGI-BP-S depression score at Week 6 comparing each SEP-4199 treatment group to placebo in ITT population with major depressive episode associated with bipolar I disease (bipolar I disorder) at sites located in US and Europe defined through the inclusion/exclusion criteria, should a subject be able to tolerate and adhere to treatment up to Week 6.

The efficacy of SEP-4199 in terms of the CGI-BP-S depression score will be evaluated using the following two null hypotheses:

H3: There is no difference in mean change from baseline at Week 6 on the CGI-BP-S depression score in the SEP-4199 200 mg treatment arm compared to Placebo.

H4: There is no difference in mean change from baseline at Week 6 on the CGI-BP-S depression score in the SEP-4199 400 mg treatment arm compared to Placebo.

The alternative hypothesis for each of the null hypotheses is that there is a difference.

The CGI-BP-S depression score will be analyzed by the MMRM method described for the primary efficacy endpoint with baseline CGI-BP-S depression score used as covariate (see [Section 16.1.3](#)) for the ITT population. LS mean of change from baseline over time will be plotted including p-value.

The CGI-BP-S mania and overall bipolar illness scores will only be presented in listings.

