0.2 Received disallowed concomitant medication

Concomitant medications are defined as any medications taken during the course of the study, with a start date on or after the date of the first dose of study drug and on or before the date (day) of the last dose of study drug; or with a start date prior to, and an end date on or after, the date of the first dose of study drug, or marked as ongoing. Medications that ended prior to the date of the first dose of study drug will be considered prior medications. Medications that started after the date of the last dose of study drug will not be considered concomitant, but will be considered post-treatment.

Protocol section 10.3 discusses the requirements on prior and concomitant medications.

All medications taken by the randomized subjects under review will be provided in a data listing. To facilitate the review, the listing will present the ATC text of *all* ATC levels. In addition, preferred drug name, reported drug name (verbatim), indication, dose level, frequency, route, the start and end dates, and a flag for the psychotropic medications *based on investigator assessment* will be included. The listing will also include flags for whether a medication is prior, concomitant, or post-treatment, and whether or not a medication started prior to the first dose of study drug.

The disposition data of all randomized subjects under review will also be provided in a data listing.

The reviewers will manually review both listings to identify any IPDs as a result of the use of disallowed

Document:

Author:

Version Number:

V2.0

Version Date:

21MAY2020

Template No: CS_TP_BS016 Revision 4
Effective Date: 01Apr2016

Reference: CS_WI_BS005

concomitant medication(s) as specified in the protocol.

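### SAP 16.1.3 defines a hypothetical effect for subjects who continue after an intercurrent event, but the primary analysis handles those subjects by treatment policy

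*SAP*

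**What the plan says.** **Estimand.** SAP 16.1.3, attribute C, bases the effect on what would be seen "in the hypothetical absence of any intercurrent events, ie, if all subjects had adhered to treatment up to Week 6". It says that this covers subjects who continue, with the example "subject received a prohibited medication during the treatment period and was not discontinued from the study". The following paragraph then sets the handling: "Any intercurrent event where subject continues the study regardless of the intercurrent event will be ignored for the primary analysis", with the efficacy data used unchanged. Only events that lead to discontinuation receive a hypothetical treatment, through the missing-at-random (MAR) assumption of the MMRM.

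**Adherence wording.** Protocol 15.3.5.1 describes the primary effect as applying "should a subject be able to tolerate and adhere to treatment for 6 weeks". SAP 16.2.3 describes the CGI-BP-S estimand as applying "should a subject be able to tolerate and adhere to treatment up to Week 6".

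**Deviations.** SAP 5.1 keeps subjects in the ITT population whatever their deviations. SAP 16.1.5.2 adds a check: "The primary MMRM analysis will be repeated for the PP population to examine the impact of protocol deviations". Under SAP 5.2, the per protocol (PP) population leaves out subjects whose important protocol deviations could affect interpretation of the primary endpoint. For medication, Appendix 7 item 0.2 states: "The reviewers will manually review both listings to identify any IPDs as a result of the use of disallowed" concomitant medication.

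**Early-termination (ET) scores.** The text of SAP 6.3 maps an ET visit to the next planned visit only when it lies inside that visit's window. Otherwise the scores go to an unscheduled visit and stay out of the MMRM. Table 1 in the same section gives day ranges for MADRS and CGI-BP-S, and SAP 16.1.2 carries the mapping into the primary analysis.

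**The concern.** An estimand should name one strategy for each type of intercurrent event, and the analysis should follow it. Here one type, an event after which the subject stays in the study, is given two. The definition says hypothetical; the handling paragraph describes treatment policy.

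As the SAP is written, the primary contrast would be reported as the effect had everyone adhered. For subjects who took a prohibited drug, received the wrong treatment or complied poorly, it is the effect with those events included. A reader of the report could not tell which was estimated, and no other planned ITT analysis would supply the first.

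The ET mapping raises a lesser question: how far the Week 6 contrast depends on scores taken before the protocol's visit window opens. No planned analysis is designed to answer it.

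**Working it through.** No figure in the plan can be reproduced for this point, so the check is mainly a comparison of texts. The only arithmetic concerns the visit windows.

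**1. Stated strategy against handling, by event type.**

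| Event in a subject who continues | Where the plan foresees it | Stated strategy (SAP 16.1.3) | Primary handling |
|---|---|---|---|
| Prohibited medication | Attribute C itself; Appendix 7 item 0.2 | Hypothetical, by name | Scores used |
| Wrong treatment | Appendix 7 item 0.3 | Hypothetical, under any event | Scores used |
| Overall compliance below 75% or above 125% | Appendix 7 item 0.4 | Hypothetical, under any event and the adherence clause | Scores used |
| MADRS or CGI-BP-S rated after unblinding | Appendix 7 item 0.6 | Hypothetical, under any event | Scores used |

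The two columns on the right disagree in every row.

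**2. Does any planned analysis estimate the stated effect for these events?**

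- Primary MMRM and ANCOVA (SAP 16.1.3, 16.1.5.1): no; scores after the event are used.
- PP MMRM (16.1.5.2): a partial check. It removes the whole subject, including scores before the event, so it addresses a different population.
- Placebo-based imputation (16.1.4.2): no; it imputes values still missing after the ET visits are remapped. A score observed after an event is not missing.
- Tipping point (16.1.4.3 and Appendix 3, Step 4): no; the penalty applies only where the original score is flagged missing.
- COVID-19 runs (16.1.4.4, 16.1.4.5): no; they remove scores by remote visit or by date, not by event.

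**3. Size.** For one dose, the distance between the two estimands at Week 6 is about

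p(dose) × g(dose) − p(placebo) × g(placebo),

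where p is the share of the arm that continues after an event and g is the mean shift in Week 6 score that the event causes. The distance is zero if the two products are equal, and it can take either sign. The documents give no p and no g. The subject counts in SAP 3.7 (3 never dosed, 4 without post-baseline data) concern exclusions from the ITT population and do not help.

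**4. ET windows.** Protocol Table 2 allows ±2 days at each visit. SAP Table 1, for MADRS and CGI-BP-S, gives:

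| Visit | Protocol window | Mapped ET days | Mapped days outside the window |
|---|---|---|---|
| Week 1 | 7 ± 2 = 5–9 | 1–9 | 1–4 |
| Week 2 | 14 ± 2 = 12–16 | 10–16 | 10–11 |
| Week 4 | 28 ± 2 = 26–30 | 17–30 | 17–25 |
| Week 6 | 42 ± 2 = 40–44 | 31–44 | 31–39 |

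A Week 6 value can therefore come from 40 − 39 = 1 to 40 − 31 = 9 days before the window opens. For Week 4 the range is 26 − 25 = 1 to 26 − 17 = 9 days. Read with the protocol window, the text of SAP 6.3 would leave these scores out; Table 1 puts them in. Once mapped they count as observed, so neither missing-not-at-random analysis reaches them. The dropout profiles (16.1.4.1) show Week 6 terminators separately but do not re-estimate the contrast. The COVID-19 runs would drop such scores only incidentally.

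**The case against.** **The handling is stated openly.** This is true. Attribute C says what will be done, a PP repeat is planned for both endpoints, and disallowed medication is reviewed blind. The fault is in the definition, not in a concealed analysis. But the PP repeat does not estimate the effect that the definition describes.

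**The adherence wording need not conflict.** A reader might infer that Protocol 15.3.5.1 and SAP 16.2.3 also contradict the handling of prohibited medication. They do not mention it, and someone who adds another drug while still taking study drug can be said to adhere. For that event the contradiction lies within SAP 16.1.3. The adherence wording does conflict with keeping the scores of non-compliant or wrongly treated subjects.

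**Few subjects may be affected.** Protocol 10.3.3 says that subjects who need restricted medication should be excluded or discontinued, which limits the number who continue. This stands as a reason to expect a modest effect, but it gives no rate.

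**A bias or loss of power might be inferred.** The documents do not support either. Any shift would rest wholly on assumed rates. It would also measure distance from an estimand that the fix gives up: once the estimand is restated as treatment policy, using these scores is correct.

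**The ET mapping is prespecified.** This is also true, and a reader should not take it for an error in the primary analysis. Removing these scores has a cost: it discards the last rating before dropout, which helps to make MAR credible. This part is therefore only an added sensitivity analysis and a clarification of SAP 6.3.

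**Conclusion.** The main point holds and should be fixed. In SAP 16.1.3 the estimand is hypothetical for any intercurrent event, expressly including prohibited medication in subjects who continue, while the analysis is treatment policy for those subjects. No planned ITT analysis estimates the stated effect for them, and the PP MMRM checks it only in part.

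The size and direction of the difference cannot be derived from the documents, and no power figure belongs with this point. The planned sample size and the primary result do not change; what changes is the description of what that result estimates. This conclusion rests on the text alone and needs no assumption about rates.

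The ET mapping is secondary. It is a disclosed choice that no planned analysis is designed to test, and the text and Table 1 of SAP 6.3 agree only if Table 1 is taken to define the window.

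**What to change.** Before unblinding:

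1. **Restate attribute C.** Use treatment policy for events after which the subject continues, and hypothetical under MAR for discontinuation. Align the adherence wording in SAP 16.1.3 and 16.2.3. List the change in SAP 3.7, because Protocol 15.3.5.1 has the same wording.
2. **Add one ITT sensitivity MMRM per endpoint.** Set MADRS and CGI-BP-S scores to missing after the first continuing event that can be dated: disallowed medication (Appendix 7 item 0.2), wrong treatment (0.3) or unblinding (0.6). Wrong treatment can be identified only after unblinding, so its rule must be written now. Low overall compliance (0.4) has no single date and stays with the PP check.
3. **Clarify the ET mapping.** State in SAP 6.3 that Table 1 defines the window, and keep the mapping in the primary analysis. Add one sensitivity MMRM per endpoint that treats ET scores outside the protocol visit window as missing, and carry this through the placebo-based and tipping-point imputations.

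**Cost.** A paragraph of SAP wording, one sentence in 6.3 and one entry in 3.7; two extra MMRM runs per endpoint and a repeat of each imputation analysis. The date of first disallowed use must come from the planned manual review, because under Protocol 10.3.3 permission depends on dose, timing and Medical Monitor approval. The sensitivity runs have slightly fewer observed values, and the ET run loses the last score before dropout for the subjects concerned.
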